13.3 Off protocol treatment

Patients who do not develop PD during cycle 1 and go off protocol treatment for reasons other than PD within any cycle will proceed to survival follow-up. Note: This does not apply to patients receiving alternative therapy. Patients who go off treatment for alternative therapy will exit the study (no follow-up).

Patients who achieve CR at any time will proceed to survival follow-up.

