4.0 Test Schedule

4.1 Test schedule for Mycosis Fungoïdes

Tests and procedures	≤ 28 days prior to registration	Active Monitoring Phase*			Follow-up*	
		prior to treatment Day 1, Cycles 2-4 ⁷	prior to treatment Day 1, Cycles 5 and beyond ⁷	End of treatment (21 days after last dose)	Clinical Follow- up (30 days after EOT)	Clinical Follow- up visit (90 days after EOT)
Main study Informed Consent	X					
Inclusion/Exclusion Criteria	X					
Demographics, medical history	X				X	
Ht and Wt**	X	X		X		
Vital signs						
Blood pressure	X	X	X	X		
Pulse						
Temperature						
Prior and Concomitant Medication Review	X				X	
Post-study Anticancer therapy status					X	X
Adverse event assessment	X	X	X	X	X	X
Physical Exam	X	X	X	X		
Dermatology Exam ^R	X	X	X	X	X	X
Standardized Clinical Photography ^R	X	X	X	X	X	X
Skin Biopsy	X	X ^R				
ECOG PS	X			X		X
mSWAT	X	X	X	X	X	X
Pregnancy test ¹	X					
Hematology group						
CBC with Diff	X	X	X	X	X	
Chemistry group ²	X	X	X	X	X	
Urinalysis	X					
PT/INR and PTT	X					
T3, FT4, and TSH ³	X	X	X	X	X	
Tumor Imaging ⁴	X		X	X		
T and B-cell Quantitation ⁵	X		X ^R	X ^R		
Mandatory Research tissue specimens (see Section 17.0) ^{6,R} ,	X	X				

Cycle = 21 days

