AEs associated with pembrolizumab exposure may represent an immunologic etiology. These immune-related AEs (irAEs) may occur shortly after the first dose or several months after the last dose of pembrolizumab treatment and may affect more than one body system simultaneously. Therefore, early recognition and initiation of treatment is critical to reduce complications. Based on existing clinical trial data, most irAEs were reversible and could be managed with interruptions of pembrolizumab, administration of corticosteroids and/or other supportive care. For suspected irAEs, ensure adequate evaluation to confirm etiology or exclude other causes. Additional procedures or tests such as bronchoscopy, endoscopy, skin biopsy may be included as part of the evaluation. Based on the severity of irAEs, withhold or permanently discontinue pembrolizumab and administer corticosteroids. Dose modification and toxicity management guidelines for AEs associated with pembrolizumab are provided in the table in Section 8.1.

9.6b Toxicity management of infusion-reactions related to pembrolizumab

Pembrolizumab may cause severe or life threatening infusion-reactions including severe hypersensitivity or anaphylaxis. Signs and symptoms usually develop during or shortly after drug infusion and generally resolve completely within 24 hours of completion of infusion. Dose modification and toxicity management guidelines on pembrolizumab associated infusion reaction are provided in the table below.

NCI CTCAE Grade	Treatment	Premedication at Subsequent Dosing
Grade 1 Mild reaction; infusion interruption not indicated; intervention not indicated	Increase monitoring of vital signs as medically indicated until the subject is deemed medically stable in the opinion of the investigator.	None

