10.8 Additional Event Reporting Instruction (Merck)

10.81 All AEs, SAEs and other reportable safety events that occur after the consent form is signed but before treatment allocation must be reported by the investigator if the participant is receiving placebo run-in or other run-in treatment, if the event cause the participant to be excluded from the study, or is the result of a protocol-specified intervention, including but not limited to washout or discontinuation of usual therapy, diet, or a procedure.

- All AEs from the time of treatment allocation/randomization through 30 days following cessation of study treatment must be reported by the investigator.
- All AEs meeting serious criteria, from the time of treatment allocation/randomization through 90 days following cessation of study treatment, or 30 days following cessation of study treatment if the participant initiates new anticancer therapy, whichever is earlier must be reported by the investigator.
- All pregnancies and exposure during breastfeeding, from the time of treatment allocation/randomization through 120 days following cessation of study treatment, or 30 days following cessation of study treatment if the participant initiates new anticancer therapy must be reported by the investigator.
- Additionally, any SAE brought to the attention of an investigator at any time outside of the time period specified above must be reported immediately by the investigator if the event is considered to be drug-related.

Investigators are not obligated to actively seek AE or SAE or other reportable safety events in former study participants. However, if the investigator learns of any SAE, including a death, at any time after a participant has been discharged from the study, and he/she considers the event to be reasonably related to the study treatment or study participation, the investigator must promptly notify Merck.

10.82 Definition of an Overdose for This Protocol and Reporting of Overdose to the Sponsor and to Merck

For purposes of this study, an overdose of pembrolizumab will be defined as any dose of 1,000 mg or greater (≥ 5 times the indicated dose). No specific information is available on the treatment of overdose of pembrolizumab. In the event of overdose, the participant should be observed closely for signs of toxicity. Appropriate supportive treatment should be provided if clinically indicated.

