13.0 Treatment/Follow-up Decision at Evaluation of Patient

Reason Off Treatment (from the Off Treatment Form)	Go to CFU, SFU, or end folder rollout
1 = Treatment (Intervention) Completed Per Protocol Criteria	CFU
2 = Patient Withdrawal/Refusal After Beginning Protocol Therapy (Intervention)	SFU
3 = Adverse Events/Side Effects/Complications	SFU
4 = Disease Progression, Relapse During Active Treatment (Intervention)	SFU
5 = Alternative Therapy	No follow-up
6 = Patient Off-Treatment (Intervention) For Other Complicating Disease	SFU
7 = Death On Study	No follow-up
8 = Other	SFU
10 = Disease Progression Before Active Treatment (Intervention)	No follow-up
24 = Patient Withdrawal/Refusal Prior To Beginning Protocol Therapy (Intervention)	No follow-up

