13.4 Clinical Follow-up

Patients achieving CR90, PR, or SD, and who have completed 24 months of treatment will be observed for clinical follow-up at 30 and 90 days after the end of treatment, and then proceed to survival follow-up.

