13.6 Duration of therapy for CR90, PR or SD

Patients who achieve CR90, PR, or SD will continue on therapy up to a maximum duration of 24 months.. After 24 months,, the patients will continue to clinical follow-up at 30 and 90 days after the last treatment and then proceed to survival follow-up (see 13.4 above). Subsequent treatment is at the discretion of their attending.

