15.1 Pembrolizumab (MK-3475, SCH 900475, Keytruda®)

15.11 Background: Pembrolizumab is a potent humanized IgG4 monoclonal antibody with high specificity of binding to the PD-1 receptor, thus inhibiting its interaction with PD-L1 and PD-L2. Based on preclinical *in vitro* data, pembrolizumab has high affinity and potent receptor blocking activity for PD-1.

15.12 Formulation:

Pembrolizumab is available as a liquid 25 mg/mL, 100 mg/vial.

15.13 Preparation and storage:

Vials should be stored in the refrigerator at temperatures between 2-8°C.

Drug concentrate is further diluted with normal saline (or 5% dextrose) in the concentration range of 1 to 10 mg/mL. The infusion solution in the IV bag should be immediately administered. Diluted pembrolizumab solutions may be stored at room temperature for a cumulative period of up to 46 hours. This includes room temperature storage of admixture solutions in the IV bags and the duration of infusion. The product can also be stored under refrigeration at 2°C to 8°C for no more than 96 hours from the time of dilution. If refrigerated, the diluted solution must be allowed to come to room temperature prior to administration. The solution must be discarded after 6 hours at room temperature or 96 hours under refrigeration.

15.14 Administration: Pembrolizumab is administered by intravenous infusion over 30 minutes via a 0.22 micron in-line filter. The final infusion volume must be between 1 and 10 mg/mL. Maximum rate of infusion should not exceed 6.7 mL/minute through a peripheral or indwelling catheter. Flush the line with 0.9% NaCL following the completion of the infusion.

15.15 Pharmacokinetic information:

- a) Absorption –Because pembrolizumab is administered intravenously, it is immediately and completely bioavailable. Steady-state concentrations of pembrolizumab are reached by 16 weeks of repeated dosing with a Q3W regimen and the systemic accumulation is 2.1-fold. The peak concentration, trough concentration, and area under the plasma concentration versus time curve at steady state of pembrolizumab increased dose proportionally in the dose range of 2 to 10 mg/kg Q3W.
- b) Distribution – Pembrolizumab has a limited volume of distribution.

- c) Excretion – CL is approximately 23% lower after achieving maximal change at steady state compared with the first dose. The terminal elimination half-life ($t_{1/2}$) is estimated to be 22 days at steady state.

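### Only patients who complete 24 months are routed to the two post-treatment visits with AE assessment; early stoppers have none scheduled after about day 21, although SAE reporting can run to day 90

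*Combined protocol and SAP*

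**What the plan says.** **Schedule.** Section 4.1 marks AE assessment at the visit headed "End of treatment (21 days after last dose)" and at two clinical follow-up visits, 30 and 90 days after EOT. The grid does not limit who attends. Those two visits are also the only ones at which post-study anticancer therapy status is collected.

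**Who gets the follow-up visits.** Section 13.4 reserves them for patients with CR90, PR or SD "who have completed 24 months of treatment will be observed for clinical follow-up at 30 and 90 days after the end of treatment". Section 13.6 keeps that restriction but describes "clinical follow-up at 30 and 90 days after the last treatment and then proceed to survival follow-up".

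**Where everyone else goes.** Under section 13.3, patients without cycle-1 PD who "go off protocol treatment for reasons other than PD within any cycle will proceed to survival follow-up". In the section 13.0 table, code 3, "Adverse Events/Side Effects/Complications", leads to survival follow-up, as do codes 2, 4, 6 and 8. The dose-modification table in 8.1 sends toxicity stops to the same place. Survival follow-up (4.2) is a three-monthly status contact covering PD, death and new primaries, with no AE item.

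**Reporting windows.** Section 10.81 requires all AEs to 30 days after cessation, and SAEs "from the time of treatment allocation/randomization through 90 days following cessation of study treatment", cut to 30 days if new anticancer therapy starts. Section 9.6a states that immune-related events may appear "several months after the last dose of pembrolizumab treatment".

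**The concern.** The reporting windows apply to every treated patient, but the visits at which a patient would be asked about events in those windows are given to one group only. That group is defined by outcome and tolerance: its members stayed on drug for 24 months without progression. A patient stopped for toxicity, in whom late immune events are of most interest, has no scheduled question after EOT.

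Safety is a secondary goal (2.21), and section 16.42 tabulates the maximum grade of each event type per patient. If late events are asked about in completers and only reported when they surface in others, the tables mix two levels of ascertainment. With accrual capped at 10, one missed patient-level event changes a frequency by 1/10, or 10 percentage points.

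The length of the SAE window also depends on whether new anticancer therapy has started, and for early stoppers no visit is scheduled to collect that fact.

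**Working it through.** The plan states no figure for this, so the check sets the routes against the schedule and then counts days.

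**Inputs**
- EOT visit: day 21 after last dose (4.1), with a ±3-day window for all visits, so days 18 to 24.
- Follow-up visits: EOT + 30 and EOT + 90 (4.1), or 30 and 90 days after last treatment (13.6).
- Reporting windows: AEs to day 30; SAEs to day 90, or day 30 with new anticancer therapy (10.81).
- Assumptions: cessation of treatment means the last dose, and patients who stop early for reasons other than PD attend EOT. Section 13.3 does not itself mention the visit.

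**Routes**

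| Reason for leaving treatment | Route | Last scheduled AE assessment |
|---|---|---|
| CR90, PR or SD at 24 months | Clinical follow-up (13.4, 13.6) | Day 111 or day 90, depending on anchor |
| Toxicity, other disease, other reason, withdrawal | Survival follow-up (13.0, 13.3, 8.1) | EOT, about day 21 |
| PD after cycle 1 | EOT at time of PD, then survival follow-up (13.2) | Time of PD |
| PD in cycle 1 | Exit, no follow-up (13.2) | Not stated |
| Alternative therapy | Exit, no follow-up (13.0, 13.3) | EOT at the latest |
| CR | Survival follow-up (schema footnote, 13.3, 13.5), but code 1 leads to clinical follow-up (13.0) | Conflict |

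**Days without a scheduled assessment.** Let W be the end of the reporting window and d the day of the last scheduled AE assessment. The uncovered stretch is W − d.

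- All AEs: 30 − 21 = 9 days, 9/30 = 30% of the window. With d from 18 to 24: 12 down to 6 days.
- SAEs, no new therapy: 90 − 21 = 69 days, 69/90 = 77%. With d from 18 to 24: 72 down to 66 days.
- SAEs, new therapy by day 30: 30 − 21 = 9 days.
- PD after cycle 1: 30 − d and 90 − d, with d the day of PD. If PD is found before day 21, the gaps exceed 9 and 69 days.

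**Anchor.** Counting from EOT, the visits fall on days 21 + 30 = 51 and 21 + 90 = 111. Counting from last treatment, they fall on days 30 and 90. The two readings differ by 21 days. On the EOT anchor both visits come after the matching window has closed. On the last-treatment anchor they coincide with the window ends, but the ±3-day allowance lets them fall as early as days 27 and 87, 3 days short.

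**The case against.** The best answer is that the plan does not leave late toxicity unwatched. AE, SAE and event-of-clinical-interest reporting applies to every treated patient (10.81, 10.84, 10.85). SAEs must be followed to outcome (10.84), which covers the serious event that caused a stop. Related SAEs beyond 30 days need expedited reports (10.4), and expedited events must also enter routine reporting (10.1). Patients are told to report side effects at once (15.191), and survival follow-up is itself a regular contact. The sentence in 10.81 releasing investigators from actively seeking events concerns former participants, and patients in survival follow-up are still on study. All of this stands. A reader might infer that early stoppers are unmonitored; the documents do not support that. What remains is that a duty to report is not a scheduled question, and only completers get the question. Section 10.7 defers late-event instructions to a Forms Packet that is not among the documents.

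Four other stronger readings also fail.
- **69 days for every early stopper.** The window closes at day 30 once new anticancer therapy starts, and PD patients have EOT at PD.
- **The 12-week limits in 8.1 as a follow-up window**, giving 84 − 21 = 63 days without a visit. Those limits decide when a patient whose drug is on hold must stop permanently. A patient already stopped has no such decision left, and a patient on hold has not yet left treatment.
- **Residual drug at day 21.** Section 15.15 gives a half-life "estimated to be 22 days at steady state", reached by 16 weeks. It does not describe patients who stop before then, and the documents do not tie immune-event risk to remaining drug.
- **CR as plainly excluded.** CR is a protocol stopping criterion (7.1), so such a stop could be coded 1 and sent to clinical follow-up. This is a contradiction, not a settled exclusion.

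Nor is the bias measured: section 16.42 plans no late-event rate, and the primary endpoint is unaffected.

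**Conclusion.** The point holds as a gap in scheduled ascertainment and should be fixed. Patients stopping early for toxicity, later PD, other disease or other reasons have their last scheduled AE assessment at EOT: about day 21 (18 to 24), or the time of PD. With EOT at day 21, that leaves about 9 of 30 AE-window days, and 69 of 90 SAE-window days (9 if new therapy starts by day 30), without a scheduled assessment. Cycle-1 PD and alternative-therapy patients leave with no follow-up at all. For cycle-1 PD this also sits awkwardly with code 4 in 13.0, which makes no cycle distinction.

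The likely direction is understatement of AE frequencies in early stoppers relative to completers; the documents give no basis for its size. The day counts assume that cessation means last dose and that early stoppers attend EOT. Two internal contradictions stand apart from these counts: the route after CR, and the anchor of the 30- and 90-day visits.

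**What to change.** Reconcile sections 4.1, 4.2, 10.81 and 13.0 to 13.6 so that:

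1. Every dosed patient who leaves treatment, for any reason, has the two already-defined post-treatment AE assessments; patients who withdraw have them only if they agree. Telephone contact is enough where a visit is not feasible.
2. Both contacts record whether new anticancer therapy has started and when, so that the SAE window can be applied.
3. The two contacts have one anchor date in 4.1, 13.4 and 13.6, with a visit window that lets them cover the 30- and 90-day limits in 10.81.
4. The CR route reads the same in the schema, 13.0, 13.3 and 13.5, and the cycle-1 PD route reads the same in 13.0 and 13.2.

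This changes data collection, not treatment. The cost is protocol wording and at most two extra contacts per early stopper in a trial capped at 10 patients. Some contacts will be missed, mainly in patients who have moved to other therapy.

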*The maximum duration of therapy is 24 months. If the patient achieves CR during this period, further pembrolizumab cycles will be discontinued and the patient will proceed to survival followup.

**Non-responders include patients with progressive, nodal, visceral, or blood disease as assessed by repeat staging after Cycle 4 and at the end of treatment visit.

Generic name: pembrolizumab, MK-3475
Brand name(s): Keytruda™
Mayo Abbreviation: MK3475
Availability: Mayo Clinic Pharmacy

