4.2 Survival Follow-up

	Survival Follow-up				
	q. 3 months until PD	At PD	After PD q. 3 months	Death	New Primary
Survival Follow-up	X	X	X	X	At each occurrence

1. If a patient is still alive 2.5 year after registration, no further follow-up is required.

5.0 Stratification Factors OR Grouping Factor:

None.

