9.52 Prohibited Concomitant Medications

Subjects are prohibited from receiving the following therapies during the Screening and Treatment Phase (including retreatment of patients who develop new skin disease after achieving a complete cutaneous response) of this trial:

- Antineoplastic systemic chemotherapy or biological therapy
- Immunotherapy not specified in this protocol
- Chemotherapy not specified in this protocol
- Investigational agents other than pembrolizumab
- Radiation therapy
 - Note: Radiation therapy to a symptomatic solitary lesion or to the brain may be allowed at the investigator's discretion.
- Live vaccines within 30 days prior to the first dose of trial treatment and while participating in the trial. Examples of live vaccines include, but are not limited to, the following: measles, mumps, rubella, varicella/zoster, yellow fever, rabies, BCG, and typhoid vaccine.
- Systemic glucocorticoids for any purpose other than to modulate symptoms from an event of clinical interest of suspected immunologic etiology. The use of physiologic doses of corticosteroids may be approved after consultation with the sponsor.

Subjects who, in the assessment by the investigator, require the use of any of the aforementioned treatments for clinical management should be removed from the trial. Subjects may receive other medications that the investigator deems to be medically necessary.

The Exclusion Criteria describes other medications which are prohibited in this trial.

There are no prohibited therapies during the Post-Treatment Follow-up Phase.

9.6 a Toxicity management for immune-related AEs associated with pembrolizumab

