11.2 Evaluation of Measurable Disease

11.21 Evaluation of primary cutaneous lesion

mSWAT is calculated using body surface area (BSA) of each MF lesion (palm plus fingers of the patient $\approx 1\%$ BSA) in each of 12 areas of the body, multiplying the sum of the BSA of each lesion type by a weighting factor (patch=1, plaque=2, and tumor =4) and generating a sum of the subtotals of each lesion subtype.

11.211 Measurement of effect

- Overall cutaneous response rate (ORR) = proportion of patients with a 50% or greater reduction of baseline mSWAT score
- Complete cutaneous response rate (CR) = proportion of patients with a 100% reduction of baseline mSWAT score
- Cutaneous 90 response rate (CR90) = proportion of patients with a 90% or greater reduction of baseline mSWAT score without the development of new tumors
- Cutaneous partial response rate (PR) = proportion of patients with a 50-90% baseline reduction of mSWAT score without the development of new tumors
- Progressive cutaneous disease (PD) = greater than 25% increase in baseline mSWAT or the development of new tumors. However, if in the judgement of the investigator, the increase in mSWAT is the result of inflammation due to treatment and/or the unmasking of subclinical skin involvement, this increase in mSWAT shall not be considered evidence of progressive cutaneous disease and the patient shall otherwise be classified as stable cutaneous disease (SD).
- Stable cutaneous disease (SD) = <25% increase to <50% reduction in baseline mSWAT without the development of new tumors ; or patients with a greater than 25% increase baseline mSWAT due to

the result of inflammation due to treatment and/or the unmasking of subclinical skin involvement.

- Relapsed cutaneous disease = Any disease recurrence in those with complete response

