11.4 Measurement at Follow-up Evaluations

11.41 Cutaneous lesions

- mSWAT will be collected at baseline, end of every cycle of treatment and during clinical follow-up at 30 and 90 days.
- mSWAT response will be recorded as per Section 11.211.

11.42 Target visceral lesions and lymph nodes.

- Subsequent PET-CT scans must be obtained after cycle 4 and the end of treatment visit following initial documentation of objective cutaneous response status of either complete response (CR) or partial response (PR).
- In the case of stable disease (SD), follow-up measurements must have met the SD criteria at least once after study entry at a minimum interval of 3 weeks.
- The cytological confirmation of the neoplastic origin of any effusion that appears or worsens during treatment when the measurable tumor has met criteria for response or stable disease is mandatory to differentiate between response or stable disease (an effusion may be a side effect of the treatment) and progressive disease.

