Duration of response is defined for all evaluable patients who have achieved a CR, CR90 or PR as the date at which the patient's objective status is first noted to be a CR, CR90 or PR to the earliest date relapse is documented. The distribution of duration of complete response will be estimated using the method of Kaplan-Meier.

Time to response is defined as the time from registration to CR, CR90 or PR. The distribution of survival time will be estimated using the method of Kaplan-Meier (Kaplan and Meier 1958).

Overall survival time is defined as the time from registration to death due to any cause. Patients are censored if they are alive at the time of analysis. The distribution of survival time will be estimated using the method of Kaplan-Meier (Kaplan and Meier 1958). In addition, the overall survival rate at 2 years after registration will be reported.

Additional Analyses: All endpoints may be analysed using patient characteristics to explore possible associations of demographics with the endpoints. Possible characteristics include clinical stage, gender and prior treatments.

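### After a complete response no skin assessment is scheduled beyond the end-of-treatment visit, so relapse can be found late or missed, and duration of response and PFS overestimated, in complete responders

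*Combined protocol and SAP*

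**What the plan says.** **Route after CR.** CR is one of the reasons to stop treatment in 7.1. Section 13.3 says "Patients who achieve CR at any time will proceed to survival follow-up", 13.5 says the same, and the footnote to the study schema says "further pembrolizumab cycles will be discontinued and the patient will proceed to survival followup". Sections 13.4 and 13.6 reserve clinical follow-up for CR90, PR or SD patients who have completed 24 months.

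**Another route.** The off-treatment table in 13.0 sends the reason "1 = Treatment (Intervention) Completed Per Protocol Criteria" to clinical follow-up.

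**Where skin is assessed.** Section 11.41: "mSWAT will be collected at baseline, end of every cycle of treatment and during clinical follow-up at 30 and 90 days". The test schedule (4.1) also marks mSWAT, dermatology exam and photography at the end-of-treatment visit, 21 days after the last dose, and at both clinical follow-up visits. The survival follow-up table (4.2) has a single row, to be completed "q. 3 months until PD", at progression and afterwards. It names no procedure and ends 2.5 years after registration.

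**What ends the endpoints.** Section 11.211: "Relapsed cutaneous disease = Any disease recurrence in those with complete response". In 16.42, duration of response runs "to the earliest date relapse is documented", and PFS runs from registration to relapse or death.

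**Retreatment.** Section 9.52 describes the treatment phase as "including retreatment of patients who develop new skin disease after achieving a complete cutaneous response". Section 13 contains no such retreatment.

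**The concern.** Goal 2.23 asks for duration of response and PFS, in a disease that section 1.0 calls incurable. Complete responders are off drug, so whether and when their skin disease returns is the main durability information that they supply. The definition of relapse is strict, since a small patch is enough, and that is the kind of event most easily overlooked without an examination. After the end-of-treatment visit, the route in 13.3 and 13.5 leaves its detection to a 3-monthly contact with no stated method.

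A relapse found late is dated late. A relapse not found leaves the patient counted as relapse-free. Both errors lengthen the estimates.

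**Working it through.** The plan gives no figure on this point, so there is none to reproduce. The check is a count from the schedule, followed by an illustration on assumed inputs.

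**Inputs from the documents.** Cycle of 21 days (4.1); treatment for at most 24 months (7.1); end-of-treatment visit 21 days after the last dose, with clinical follow-up 30 and 90 days after that visit (4.1); survival follow-up every 3 months, to 2.5 years = 30 months (4.2). A month is taken as 30.4375 days.

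**Step 1: count of scheduled skin scores.** With CR at the end of cycle c:

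- month of CR = c × 21 / 30.4375
- months without scheduled skin assessment = 30 − month of CR − 21/30.4375 (= 0.69)
- 3-monthly contacts = whole part of (30 − month of CR)/3
- for scale, further end-of-cycle scores had treatment continued to 24 months: 24 × 30.4375 / 21 = 34.8, so 34 − c

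| | CR at end of cycle 4 | CR at end of cycle 9 |
|---|---|---|
| Month of CR | 2.76 | 6.21 |
| Further scheduled mSWAT under 13.3/13.5 | 0 or 1 | 0 or 1 |
| Months with none after that | 30 − 2.76 − 0.69 = 26.6 | 30 − 6.21 − 0.69 = 23.1 |
| 3-monthly contacts in survival follow-up | 9 | 7 |
| Further cycle scores had treatment continued | 30 | 25 |

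The entry is 0 or 1 because the pre-dose visit counts as the end of the previous cycle (4.1, footnote 7). The end-of-treatment visit can then be the same visit at which CR is found. In that case the unassessed time is 30 − 2.76 = 27.2 or 30 − 6.21 = 23.8 months.

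**Step 2: the code 1 route.** If CR is coded as completion per protocol criteria, two scores are added, the last one 90/30.4375 = 2.96 months after the end-of-treatment visit. The unassessed time falls to 26.6 − 2.96 = 23.6 or 23.1 − 2.96 = 20.1 months. It is shorter but not closed.

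**Step 3: effect on the curve (illustration).** Let S be the true relapse-free proportion at 12 months, f the share of responders who are in CR, and m the share of CR relapses never found. Assume that the others are found by the next 3-monthly contact, that unfound relapses are carried as relapse-free beyond 12 months, and that loss of response in other responders is fully recorded. Then

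observed proportion = S + f × m × (1 − S).

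With exponential durations and f = 0.25 to 0.50:

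| True median (assumed) | S | m = 0.5 | m = 1 |
|---|---|---|---|
| 6 months | 0.25 | 0.34–0.44 | 0.44–0.62 |
| 12 months | 0.50 | 0.56–0.63 | 0.63–0.75 |
| 18 months | 0.63 | 0.68–0.72 | 0.72–0.82 |

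Example: 0.50 + 0.25 × 0.5 × 0.50 = 0.56. A simulation under the same assumptions gave the same values. In complete responders alone (f = 1), a true 0.50 with half of the relapses missed reads 0.50 + 0.5 × 0.50 = 0.75. The medians, f and m are all assumptions; the documents give none of them.

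**Step 4: who else is affected.** The 13.0 table also sends patients to survival follow-up for withdrawal, adverse events, other complicating disease and other reasons. Responders who stop early in these ways have the same gap.

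**The case against.** The strongest reply is that disease status is pursued after CR. Survival follow-up runs until progression and has a column for it, and 18.5 requires documentation of all sites of progression and accepts a dermatology note. Section 18.1 refers to a separate Data Submission Schedule that may say what each contact collects. This stands against the stronger reading that a reader might infer, namely that relapse after CR is not looked for at all. It does not close the gap: 18.5 governs how progression is documented once found, and 4.2 states no way of finding it.

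A second reply is that a complete responder coded 1 in the 13.0 table does get two clinical follow-up visits with mSWAT. So it would be wrong to say that the documents settle on no further skin score. They contradict each other, and two coders could treat identical patients differently.

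A third reply concerns comparison. It is tempting to conclude that complete responders look better than CR90 or PR patients, who are scored every 3 weeks on treatment. The documents do not support that. The 3-weekly scoring lasts only while they stay on treatment, and 11.211 defines relapse only after CR. The event that ends duration of response for CR90 and PR is therefore undefined, and no relative bias can be derived.

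Finally, these are secondary endpoints in a trial capped at 10 patients. Dermatology exams and photography are research funded (4.1, 19.2), and accrual was stopped by a funding decision (16.1). This argues against making in-person 3-monthly scoring a requirement. It does not argue against settling the route and stating a censoring rule.

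**Conclusion.** The point holds in this form. Under 13.3 and 13.5, no skin assessment is scheduled after CR beyond the end-of-treatment visit, while any recurrence ends duration of response and PFS. Relapse in complete responders can be found late or missed, so both endpoints can be overestimated in them. The unassessed time is about 27 months for a CR at the end of cycle 4 and about 23 months for one at the end of cycle 9, or about 3 months less if the code 1 route is followed.

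The size of any bias depends on the number of CRs, the relapse rate and the share of relapses missed, none of which the documents give; the figures in the illustration show direction and scale only. Responders who stop early for other reasons and enter survival follow-up share the gap. No bias relative to CR90 or PR patients is claimed.

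Separately, the 13.0 table conflicts with 13.3 and 13.5, and 9.52 conflicts with section 13 on retreatment. Both need reconciling.

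**What to change.** 1. **Route.** Reconcile 13.0 (code 1), 13.3, 13.4, 13.5 and the schema footnote so that CR patients attend the existing 30- and 90-day clinical follow-up visits, with dermatology exam, photography and mSWAT, before survival follow-up.
2. **Analysis (16.42).** Treat a relapse reported after those visits as interval-censored between the last clear mSWAT and the report. With so few patients, two Kaplan-Meier curves, one with relapse dated at each end of the interval, would serve.
3. **Censoring (16.42).** Censor relapse-free CR patients at their last documented skin assessment, at least as a sensitivity analysis. This leans the other way, since a reported relapse still counts while a relapse-free patient leaves the risk set early. Show it beside the analysis that carries such patients to last contact.
4. **Retreatment.** Reconcile the 9.52 wording with section 13. Which rule should apply is not a statistical question.

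**Cost.** Two extra research-funded skin visits per CR patient. The number of CRs is unknown: 2 to 6 visits for an assumed 1 to 3 CRs, and at most 2 × 10 = 20. The analysis rules need no visit, but uncertainty in duration of response will be wider. In-person mSWAT at the 3-monthly contacts would shorten the gap further; it is optional, because 4.2 does not say that those contacts are visits.
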